10 STUDY DESIGN

This is an open-label, PoC pilot study in which patients are supplemented with pramipexole for 10 weeks. The study is being conducted in Lund, at Psychiatry Skåne, Adult Psychiatry Lund as a single center study. The treatment study is supplemented with a sub-study with fMRI examination in research subjects who wish to participate in this (not mandatory to be included in the main study).

11 STUDY POPULATION

Fifteen research subjects with either unipolar depression, bipolar disorder in depressive phase, or dysthymia are recruited to receive pramipexole treatment. All research subjects are asked to participate in the substudy (fMRI examination). Patients from the outpatient clinics and inpatient wards at the psychiatry in Lund will be asked if they want to participate in the study by treating physicians. Only those who are cared for under the Health and Medical Services Act (i.e. not under compulsory care) may be considered for the study. After the patient has been informed of the study and given consent, the patient will be invited to *screening* visits to the doctor responsible for research at the research clinic or the research physician visits the patient in the ward where the patient is admitted. All examinations/visits in connection with the study will take place at the adult psychiatry in Lund, while the fMRI examination will take place at Skåne University Hospital in Lund.

Research subjects who meet all inclusion criteria and no exclusion criteria as set out below, may be included in this study.

11.1 ELIGIBILITY CRITERIA

11.1.1 Inclusion criteria

1. Age ≥ 18 years ≤ 75 years.
2. Diagnosis of; unipolar depressive episode or bipolar disorder in depressive phase or dysthymia.
3. Depression symptoms: total score ≥ 18 , as measured by the Montgomery-Åsberg Depression Rating Scale (MADRS).
4. Anhedonia symptoms: total score < 27 , as measured by the Dimensional Anhedonia Rating Scale (DARS). (Low score = high level of anhedonia symptoms)
5. Have an ongoing treatment of at least one antidepressant medication ≥ 4 weeks without a dose change. For patients with bipolar disorder, there must also be ongoing treatment with mood-stabilizing drugs.
6. The research subject has signed informed consent to participate in the study.

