Method description	
Patients will be recruited from outpatient psychiatric clinics or inpatient wards. Those who meet the inclusion criteria and none of the exclusion criteria will, at the screening visit, undergo a baseline assessment including self-report rating scales and blood sampling for inflammatory markers (CRP, IL-6, TNF-alpha, white blood cells).
 
Participants who also consent to the substudy will undergo an fMRI examination of the brain's reward system (MID task). Thereafter, study treatment will begin according to the protocol, with dose escalation once weekly until treatment effect, maximum dose, or intolerable side effects occur. In the event of intolerable side effects, the participant will return to the last tolerable dose. A new attempt at dose escalation may be made after seven days, up to a maximum of two attempts. If serious adverse events occur, the medication will be tapered off.
 
After ten weeks of pramipexole treatment, a final visit will be conducted including new assessment with self-rating scales and blood samples as at baseline visits (including new fMRI examination for those participating in the substudy).

Financing	
The study is financed by funds from ALF, the Söderström-Königska Foundation, SUS Donations and Foundation and the Royal Physiographic Society in Lund.

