12 STUDY DESIGN

Visit	Screening	Baseline (last two weeks after Screening)	v1, v3, v5, v7, v9 +/- 2 days	V2, V4, V6, V8 +/- 2 day	v10 (termina tion) +/- 2 day	Follow-up during Tapering (v14) +/- 2 days
Informed consent	X					
Anamnesis	X					
MINI	X					
SUAS	X					
SHAPS		X		X	X	
MAP-SR		X		X	X	
GAD-7		X		X	X	
YMRS		X		X	X	
PGSI	X	X		X	X	
Insomnia Severity Index		X		X	X	
Fatigue Severity Scale		X		X	X	
Apathy Evaluation Scale		X		X	X	
Physical examination	X					
Blood pressure control	X			X	X	
Incl./exclusion criteria	X	X				
Blood tests β-hCG (if female of childbearing potential), eGFR, liver status, Hb.	X				X	
Inflammation tests (CRP, leukocytes, IL-6, TNF-alpha)		X			X	
fMRI (sub-study)		(X)			(X)	
Distribution of study product		X		X	(X)	
MADRS	X	X		X	X	
DARS	X	X		X	X	
Telephone contact			X			X
Incidents (AEs)			X	X	X	X

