12.1 RECRUITMENT/SCREENING

Physicians and nursing staff at general psychiatric clinics and inpatient wards (Region Skåne) are informed about the study and its inclusion criteria. Patients are asked to participate in the study. We will also advertise research subjects. Contact is made with the physician responsible for the patient (PAL) to ensure that he or she is prepared to possibly take responsibility for tapering or continued treatment with pramipexole after the end of the study (tapering can also take place within the framework of the study). The research subject is contacted for booking of *screening* visits that take place at the research clinic. During the visit, anamnesis is recapitulated, somatic diseases, ongoing drug treatment and psychiatric status is performed. Clinical suicide risk assessment is based on psychiatric status and with the help of *Suicide Assessment Scale (SUAS)*²⁷. In *Mini International Neuropsychiatric Interview (MINI)*²⁸ is done for the purpose of confirming (or rediagnosing) psychiatric diagnoses. Assessment of symptoms is made using the MADRS rating scales²⁹ (depression symptoms) and DARS³⁰ (anhedonia symptoms). Inclusion and exclusion criteria are systematically assessed and the research subject's initials and year of birth as well as the time of *screening*-visits are documented (*screening*-log). Each research subject is identified by a unique number (enrollment log). The research subject must provide a blood sample in connection with the screening visit (β -hCG [if woman of childbearing potential], eGFR, liver status and Hb). These samples must be checked before a baseline visit can be considered. The research subject will also provide blood samples in connection with the baseline visit for analysis of inflammatory markers (CRP, leukocytes, IL-6 and TNF-alpha). No biological samples are collected for later analysis. A clinical control of status and pulmonary status is performed (including anamnestic questions with a focus on heart disease and auscultation of COR/pulm and blood pressure), and a note is written in the research subject's medical record. If the research subject is to participate in an fMRI examination, information about the procedure is distributed. Before the *baseline* visit has been made, it is ensured that the blood test results (of hCG, eGFR, liver status and Hb) are assessed and cancel the visit if these are abnormal (referral to the appropriate health care provider for further investigation/action is then sent if necessary).

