12.3 PRIOR TO STUDY TREATMENT - *BASELINE*

In connection with the baseline visit, blood samples are taken for TNF-alpha, IL-6, CRP and Leukocytes. New estimation with MADRS and DARS is performed and with *Generalized Anxiety Disorder 7 scale* (GAD-7; anxiety symptoms), *Insomnia Severity Index*³¹ (sleep problems), Fatigue Severity Scale³² (fatigue symptoms), *Apathy Evaluation Scale*³³ (AES; apathy), Snaith-Hamilton Pleasure Scale³⁴ (SHAPS) The Motivation and Pleasure Scale (MAP-SR)³⁵ (anhedonia symptoms), and with the Young Mania Rating Scale (YMRS) (manic symptoms)³⁶. Study drugs will be dispensed, and the study participant will begin treatment during the day (before bedtime) with the up-titration schedule described in section 13.3. A diary for dosage is handed out and the patient is instructed to bring this filled in at the next visit. On the same day as the start of pramipexole treatment, an fMRI examination is performed for the research subjects as Participating in Sub-studies. On X-ray department Ensures that there are no contraindications

to fMRI (no magnetic implants, normal renal value). Execution of fMRI examination is described in section 26.1. The research subject spends approximately one hour in the scanner and receives compensation for participation after the survey (see section 20.5).

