13.4. NON-INVESTIGATIONAL MEDICINAL PRODUCTS

The research subject should be on a stable dosage for at least four weeks prior to the start of treatment (not ongoing dose changes) of at least one antidepressant. People with bipolar disorder should also be given a mood stabilizing drug.

To ensure that any clinical effect is dependent on pramipexole, it is recommended that study participants do not alter their ongoing antidepressant or mood stabilizing medication during the study. If the investigator, PAL or the patient himself assesses that the clinical condition nevertheless requires an adjustment of standing medication, this should of course be done. Nevertheless, the study participant can continue with pramipexole as planned, the change is noted in the patient's study log, and this is taken into account in the data analysis.

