14.1 EFFICACY VARIABLES

Total score DARS (primary variable) and exploratory variables such as total score MADRS, SHAPS, MAP-SR, GAD-7, AES, *Fatigue Severity Scale* and *Insomnia Severity Index* gathered in a self-assessment questionnaire (validation of Swedish translation of DARS is in progress) at *screening-visit baseline*-visits and every other week for 10 weeks in connection with visit at the research clinic (a total of six occasions; MADRS and DARS on seven occasions).

Blood inflammation parameters (CRP, IL-6, TNF-alpha, and leukocytes) are collected at *baseline* and final visits. Other exploratory variables are collected during the fMRI examination.

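### Does leaving the visit for the DARS < 27 criterion unstated bias the single-arm change in DARS?

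*Combined protocol and SAP*

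**What the plan says.** Criterion 4 in section 11.1.1 requires "Anhedonia symptoms: total score < 27", with low scores meaning more anhedonia, and does not say at which visit the score is taken.

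The narrative points to screening. Section 12.1 has MADRS and DARS rated at the screening visit and then states "Inclusion and exclusion criteria are systematically assessed". For the baseline visit, section 12.3 says only "New estimation with MADRS and DARS is performed", with no threshold and no consequence for eligibility.

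The schedule in section 12 is less clear. Its row "Incl./exclusion criteria" is ticked at screening and again at baseline, as are the DARS and MADRS rows.

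The synopsis blurs the two visits: "Those who meet the inclusion criteria and none of the exclusion criteria will, at the screening visit, undergo a baseline assessment". Section 14.1 shows that they are separate, with ratings on "a total of six occasions; MADRS and DARS on seven occasions". Seven is screening, baseline and weeks 2, 4, 6, 8 and 10.

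The primary comparison is baseline against week 10 (section 9.1), by two-sided paired t-test (section 16.3), with no control group (synopsis, study design).

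**The concern.** A patient who scores 24 at screening and 29 at baseline could be treated by an investigator following section 12.1 and turned away by one reading the schedule row literally. On the second reading, every starting value in the primary analysis must lie below 27. Some of those scores are low by chance and will drift back up by week 10 without any drug effect. There is no control arm to subtract that drift, and the plan does not mention it.

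Two stated aims would be touched: finding an anti-anhedonic signal, and describing the DARS distribution before and after treatment for the sizing of a later trial. The bias would also seem easy to avoid, because a separate pre-treatment DARS is already planned.

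**Working it through.** **Inputs from the documents.** Cut-off 27 (11.1.1); SD 13.73, r = 0.5, n = 10 completers of 15 enrolled, planning difference 16.6 at 95% power (16.1); screening to baseline at most two weeks (12).

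**Assumptions, not in the documents.** Pool mean DARS, screening-to-baseline correlation, scale range 0 to 68, zero drug effect.

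**The plan's own figure.** SD of change = 13.73 × √(2 × (1 − 0.5)) = 13.73. The normal approximation gives n = (1.960 + 1.645)² × (13.73/16.6)² = 8.9. The exact paired t-test at n = 10 has 92.4% power for 16.6 and needs 17.66 for 95%; at n = 11 it needs 16.61. The stated figure is close enough to serve as a yardstick here.

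**Direction.** If selection fell on the baseline score alone, the expected rise with no drug effect would be (1 − r) × SD × φ(a)/Φ(a), with a = (27 − pool mean)/SD. For a pool mean of 27 and r = 0.5 this is 0.5 × 13.73 × 0.798 = 5.5 points; for means of 35 and 40 it is 8.3 and 10.2. The sign is always positive.

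**Cut-off at both visits against screening only.** These results come from a simulated trivariate normal (screening, baseline, week 10), rounded and clipped to 0–68. Screening–baseline r is 0.8. The baseline–week-10 correlation is set so that it equals 0.5 among patients below 27 at both visits. The screening–week-10 correlation equals the smaller of the other two.

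| Pool mean | Both visits | Screening only | Difference | Baseline ≥ 27 under screening only |
|---|---|---|---|---|
| 22 | 1.92 | 0.67 | 1.25 | 15% |
| 27 | 2.16 | 0.59 | 1.57 | 21% |
| 32 | 2.23 | 0.34 | 1.89 | 27% |
| 37 | 2.21 | 0.00 | 2.21 | 34% |

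The third column is what restricting the cut-off to screening would remove: 1.25/16.6 = 8% to 2.21/16.6 = 13% of the planning difference. Favourable rejections, nominally 2.5%, are 7.9–11.6% with both cut-offs and 2.5–3.8% with screening only at n = 10. At n = 15 they are 10.7–16.6% and 2.5–4.3%.

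**Sensitivity to the correlation pattern.** The near-zero drift under screening-only selection follows largely from letting the screening score predict week 10 almost as well as it predicts baseline. If correlation fades with time (screening–week-10 r equal to the product of the other two), the shifts at pool means 22 and 37 are 3.0 against 2.1 and 4.8 against 3.5. The removable part is then 3.0 − 2.1 = 0.9 to 4.8 − 3.5 = 1.3 points, or 6–8% of 16.6. Favourable rejections at n = 10 remain 8–19% under screening only.

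**Sensitivity to the meaning of r = 0.5.** Section 16.1 does not say whether r applies to enrolled patients or to an unselected pool. On the pool reading, with means 27–40 and screening–baseline r 0.5–0.8, both cut-offs give 4.1 to 9.8 points and screening only 0 to 6.1. The difference ranges from 2.2 to 7.3 points, the top being 44% of 16.6.

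**Which reading the text supports.** One schedule row covers six inclusion and fourteen exclusion criteria. Several of these need a second look on the day treatment starts. Section 13.4 counts medication stability back from that day: "The research subject should be on a stable dosage for at least four weeks prior to the start of treatment". The gambling index is rated at baseline, and pregnancy or suicidality may have changed. Laboratory results explain the tick less well, because section 12.1 says "These samples must be checked before a baseline visit can be considered". The baseline tick therefore has ordinary uses without a second DARS threshold.

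**The case for a change.** The case for amending is that the silence is real, that it touches the primary endpoint of a study with no control arm, and that one phrase in section 11.1.1 and a note under the schedule would settle it without any new measurement. In every scenario run, the second cut-off moved the change upward and screening-only selection moved it less.

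The direction stands, and so does the observation that no sentence limits what the baseline tick covers. Three things weaken the case for a required change.

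- The bias depends on a reading that the narrative does not support. No sentence applies the DARS threshold at baseline.
- Screening-only selection is not clearly better. On the tabulated assumptions, 15–34% of those enrolled (0.15 × 15 = 2.3 to 0.34 × 15 = 5.1 patients) would start treatment at or above the cut-off, in a study of pronounced anhedonia. Confirming severity at baseline is a reasonable alternative, and statisticians could differ on it.
- A note confined to criterion 4 would leave the same question open for criterion 3. MADRS ≥ 18 also names no visit, and MADRS is also rated again at baseline.

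**Conclusion.** No change to the plan is called for. The unstated visit is missing detail that the narrative fills sensibly: eligibility is judged at screening, and the new baseline DARS is the comparator. The synopsis phrase that puts the baseline assessment at the screening visit is a wording slip, contradicted by sections 12, 12.3 and 14.1.

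On that reading the extra shift from a second cut-off does not arise. If a site did apply the cut-off twice, the addition would be about 1.3 to 2.2 points on the tabulated assumptions, 0.9 to 1.3 if correlation fades, and up to 7.3 if r = 0.5 is read as a pool correlation. Only the direction is firm; the documents give neither the pool mean nor the screening-to-baseline correlation.

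Restricting the cut-off to screening need not remove the drift either: 2.1 to 3.6 points remain when correlation fades. Regression to the mean, expectancy and natural course all sit inside the change score of an open-label, single-arm pilot. The plan declares that design, attaches no decision rule to the p-value, and defers the efficacy question to a placebo-controlled trial.

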Study population	
Inclusion (not exhaustive list): Age between 18 years and 75 years Diagnosis of unipolar depressive episode, bipolar disorder in depressive phase or dysthymia. Moderate to severe depression but with pronounced symptoms of anhedonia. To be able to participate, you must have an ongoing stable treatment with at least an antidepressant/mood stabilizer for at least 4 weeks.
 
Exclusion (not exhaustive list): Current pregnancy, breastfeeding or planned pregnancy. High suicidal. Substance abuse. Psychotic disorder. Compulsory treatment (LPT). Impulse control disorder. Diagnosis of moderate/severe renal failure or severe cardiovascular disease. Recently started psychotherapy. Ongoing ECT treatment.

Study design	
Proof of concept study, in which fifteen research subjects are included and receive study treatment (no placebo or control group occurs). All included research subjects will also be asked to participate in the substudy for fMRI examination before and after 10 weeks of treatment with pramipexole.

Timetable	
Study start: 1 September 2019 Study end: 1 December 2020.

Statistical considerations	
The objective of the study is to demonstrate feasibility (proof of concept) and we hope to generate preliminary data that will form the basis for a larger, definitive, randomized controlled trial. Specifically, we are interested in investigating: i) can we pick up a signal in our material that pramipexole has an anti-anhedonic effect in this study population, (ii) if the treatment doses we propose are reasonable: treatment effect versus side effects, iii) what the distribution looks like for DARS before and after treatment in order to optimize future dimension calculations.

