13.5 CONCOMITANT MEDICATION

Other drugs prescribed by the research subjects are managed as usual through their respective clinics. All concomitant medication is allowed while the research subjects are included in the study, except for those drugs that fall under exclusion criterion no. 11, i.e.:

- (i) ongoing treatment with medicinal products that affect plasma levels of pramipexole; For example, cimetidine, amantadine, mexilepine, zidovudine, cisplatin, quinine and procainamide.
- (ii) ongoing treatment with medicinal products that have a similar or antagonistic mechanism of action to pramipexole; For example, MAOIs, levodopa, other dopamine agonists, metoclopramide (Primperan), buspirone; This also applies to central stimulants such as methylphenidate and amphetamines (not caffeine).
- (iii) ongoing treatment with neuroleptics; For example, olanzapine, haloperidol, risperidone, clozapine, aripiprazole, quetiapine (Seroquel).

After a *wash-out* of > 14 days of all drugs, a patient can be included in the study.

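### The four-week stability rule binds only one antidepressant: mood stabilisers are covered in the synopsis but not in criterion 5 or 13.4, and second antidepressants are covered nowhere

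*Combined protocol and SAP*

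**What the plan says.** Three sections of the protocol describe the background treatment needed for entry.

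- **Section 11.1.1, criterion 5:** "Have an ongoing treatment of at least one antidepressant medication ≥ 4 weeks without a dose change". It continues: "For patients with bipolar disorder, there must also be ongoing treatment with mood-stabilizing drugs". The second sentence gives no minimum duration and no stable dose.
- **Section 13.4:** participants need "a stable dosage for at least four weeks prior to the start of treatment (not ongoing dose changes) of at least one antidepressant", and "People with bipolar disorder should also be given a mood stabilizing drug". Again the four weeks belong to one antidepressant.
- **Section 5 (Synopsis, study population):** "you must have an ongoing stable treatment with at least an antidepressant/mood stabilizer for at least 4 weeks".

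Section 13.4 also gives the purpose of stable background treatment: "To ensure that any clinical effect is dependent on pramipexole". To that end, "it is recommended that study participants do not alter their ongoing antidepressant or mood stabilizing medication during the study". Changes made during the study are to be logged and considered in the analysis, but no method is given.

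Section 16.3 makes the primary analysis a two-sided paired t-test of DARS between baseline and week 10, with no adjustment for co-medication. There is no control group.

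**The concern.** In a single-arm before-after comparison, stable background treatment is one of the few protections against crediting the study drug with another drug's effect, and section 13.4 uses it for that purpose. Read literally, the entry rule protects less than that purpose requires. A bipolar participant whose mood stabiliser was started or increased days before baseline meets criterion 5 if one antidepressant has been unchanged for four weeks. So does any participant who has just added a second antidepressant. A delayed effect of such a change would fall between baseline and week 10 and count in the primary DARS difference.

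The protocol recognises this kind of confounding elsewhere: exclusion 9 rules out psychotherapy started within six weeks. The difference in wording also means that staff working from the synopsis and staff working from criterion 5 could decide differently about the same candidate.

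**Working it through.** **Step 1: the three sections side by side**

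| Question | Synopsis | Criterion 5 | Section 13.4 |
|---|---|---|---|
| Four stable weeks for one antidepressant? | Yes, or for a mood stabiliser | Yes | Yes |
| Four stable weeks for the mood stabiliser? | Wording extends to it | No, ongoing only | No |
| Four stable weeks for a second antidepressant? | No | No | No |
| Mood stabiliser alone sufficient? | Can be read so | No | No |

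Rows 2 and 4 are disagreements between sections. Row 3 is a gap that all three share.

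**Step 2: does another section close the gap?**

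- Exclusion 11 lets the investigator exclude for concomitant drug therapy that affects evaluability. It is discretionary, points to the list in section 13.5, and sets no window for recent changes.
- Section 12.1 reviews ongoing medication at screening but sets no rule on recent changes.
- Section 12.5 and the logging rule in 13.4 concern changes during the study, not before baseline.

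None of these supplies a stability window.

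**Step 3: the plan's own figure**

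Section 16.1 uses SD 13.73, r = 0.5, two-sided α = 0.05 and n = 10, and states a detectable difference of 16.6 at 95% power. The SD of the change is 13.73 × √(2 × (1 − 0.5)) = 13.73. The exact two-sided paired t calculation gives a detectable difference of 17.66 at n = 10, with 92.4% power at 16.6; at n = 11 it gives 16.61. The stated figure is therefore reproduced to within one participant. The present point does not depend on it.

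**Step 4: possible size**

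Assumptions, not document figures: m participants each gain g DARS points from a recent background change, with m = 1 to 3 and g = 5 to 17. The upper value equals one point on each of the 17 items, which section 16.1 regards as clear improvement. The number analysed lies between 10 (the planned minimum of completers) and 15 (all enrolled, since section 16.2 makes the full analysis set primary).

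Mean shift = m × g / n.

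Observed mean change needed for significance = t(0.975, n − 1) × 13.73 / √n:

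- n = 10: 2.262 × 13.73 / √10 = 9.8
- n = 15: 2.145 × 13.73 / √15 = 7.6

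The last column is the chance of a significant improvement if pramipexole has no effect, nothing else changes and the SD of the change stays at 13.73. The nominal value in that direction is 2.5%.

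| n | m | g | Mean shift | Chance of significant improvement |
|---|---|---|---|---|
| 10 | 1 | 5 | 0.5 | 3.2% |
| 10 | 1 | 17 | 1.7 | 5.4% |
| 10 | 3 | 5 | 1.5 | 5.0% |
| 10 | 3 | 10 | 3.0 | 9.0% |
| 10 | 3 | 17 | 5.1 | 18.2% |
| 15 | 1 | 5 | 0.3 | 3.1% |
| 15 | 1 | 17 | 1.1 | 4.8% |
| 15 | 3 | 5 | 1.0 | 4.5% |
| 15 | 3 | 17 | 3.4 | 14.3% |

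**Step 5: what later removal would cost**

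If three of ten participants are set aside, the threshold for the remaining seven is 2.447 × 13.73 / √7 = 12.7 points, against 9.8 with all ten. A sensitivity analysis is possible but imprecise, so preventing the problem at entry is better.

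**The case against.** The strongest reply is that this is an openly uncontrolled pilot, meant to look for a signal before a placebo-controlled trial. Without a control arm, change cannot be attributed securely to pramipexole under any stability window. That is true, and it limits how much the fix can achieve. It does not explain why the protocol's own safeguard should cover only one drug.

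The synopsis list is labelled as not exhaustive, and section 11 directs eligibility to the full criteria. The slash may simply be compressed wording. This makes the conflict easy to repair, but a summary that omits items should still not word a listed one differently.

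DARS and MADRS are measured at both screening and baseline, so some drift before treatment would be visible. This helps, but an effect that emerges after baseline would not show there.

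A reader might infer more than the text supports:

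- **That the synopsis conflict is what lets second antidepressants through.** It is not. The synopsis also requires only one stable drug, so the second-antidepressant gap is separate.
- **That the neuroleptic rule in section 13.5 is part of the error.** There, after a wash-out "of > 14 days of all drugs, a patient can be included in the study". This is an explicit choice, and the documents give no direction for the effect of stopping such a drug on DARS.
- **That the bias could never be dealt with afterwards.** If recent changes are recorded, the affected participants can be left out in a sensitivity analysis.

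**Conclusion.** The point stands as a gap in the entry rule and an inconsistency that should be corrected. Criterion 5 and section 13.4 give mood stabilisers no stability period, the synopsis wording does, and no section covers a second antidepressant. Following the criteria as written can admit participants with just-changed background drugs, contrary to the aim stated in section 13.4.

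The effect on the primary result is unknown and probably modest. Under the assumptions above, the mean shift is 0.5 to 5.1 DARS points at n = 10 and 0.3 to 3.4 at n = 15. It would be tempting to conclude that recent background changes could by themselves produce a positive trial. The figures do not support that: every shift in the range stays below its threshold (9.8 or 7.6), and the chance of a significant improvement stays below 20% even in the extreme case. The shift would, however, add to any other change in the same direction.

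These sizes rest on an assumed number of affected participants, an assumed gain, and the planning SD of 13.73. The documents give neither the frequency of recent medication changes nor their effect on DARS.

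**What to change.** 1. Reconcile the synopsis, criterion 5 and section 13.4 so that the existing four-week no-change window applies to every ongoing antidepressant and mood stabiliser, counted back from baseline and covering starts, stops and dose changes.
2. State once, identically in all three places, whether a mood stabiliser alone qualifies.
3. Record in the CRF the date and nature of any change to a background psychotropic drug within that window, including a neuroleptic that was stopped. The wash-out in section 13.5 need not change for this purpose.
4. Add to section 16.3 a sensitivity analysis of the primary variable without participants who had such a change.

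The cost is amendment wording, one CRF item and one additional analysis. Some candidates would wait up to four weeks before inclusion. The documents give no recruitment figures, so how many cannot be stated.
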